The hypothesis under investigation in this study is that a subgroup of depressed outpatients experience brain opioid signaling dysfunction, which manifests behaviorally as increased physical and emotional pain sensitivity, and will be predictive of greater response to tianeptine (i.e., due to its mu-opioid receptor agonism). In addition to the imaging procedures described above, this hypothesis will be further studied by having participants complete a assessment battery testing pain functioning at baseline and study endpoint, in addition to further weekly assessments of selected measures.

All subjects will complete the baseline evaluation, which includes psychiatric assessments (HARS, STAI, IDS-SR, CGI, MMSE), physical pain tests (Thermal Sensitivity Test, BPI, Physical and Psychological Pain Scale), as well as emotional pain and interpersonal wellbeing tests (ARSQ, C-SSRS, Psychache scale, Perceived Stress Reactivity Scale (PSRS), Perceived Stress Scale, Shyness and Sociability Scale, Reaction to Implied Rejection Measure, Hurt Feelings Questionnaire, Multidimensional Scale of Perceived Social Support)

2.5. Summary of visit schedule and other study assessments.

As described above, at Screening, patients who decide to participate by signing informed consent will undergo a psychiatric clinical interview, and eligibility is determined by assessments with the Structured Clinical Interview Diagnostic for DSM 5 (SCID) and 24-item Hamilton Rating Scale for Depression (HRSD). Eligible subjects will complete screening laboratory tests and those currently taking other antidepressant medications will be tapered off under the supervision of the research staff according to standard clinical practice or by the doctor currently prescribing the medication. There will be a 5 day wash-out period from the time the previous antidepressant has been stopped before tianeptine is started, 3 weeks if the previous antidepressant was a monoamine oxidase inhibitor and 4 weeks if the antidepressant was fluoxetine. For participants requiring an antidepressant taper, the screening psychiatric assessments will be repeated post-

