5.1 Sample Size Determination

With total sample size of 75 subjects, we have >80% power to detect an effect size for a change in HRSD (from week 0 to week 8) of at least (Cohen's) $d = 0.33$ (small-medium), using a 2-sided test with a 5% significance level. With this sample size we can construct 95% confidence intervals for the response/remission rates that are no more than 25 percentage points wide. For our subgroup analyses to examine the hypothesis that baseline pain (physical or emotional) will differentially relate to improvement in depression, assuming a median split (low/high, $n = 37/38$) for a given physical or emotional pain battery score, we have >80% power to detect an effect size for a difference in change in HRSD (low group vs. high group) of at least $d = 0.66$ (medium-large), using a 2-sided test with a 5% significance level. Similarly, we have >80% power to detect differences in proportions of responders/remitters between the pain groups that are at least 30 percentage points. As an example, if depression response/remission is 10% in the low pain group and 40% in the high pain group, we have 86% power to find this statistically significant at the 5% significance level.

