5.2 Statistical Methods

Descriptive analyses for all variables collected at all time points will be conducted both overall and by study site. If differences are found between the study sites on outcomes of interest, then study site will be adjusted for in the analyses. For the intent-to-treat sample (i.e. those who started on drug at week 1 regardless of compliance across the 8 weeks), we will report proportions of responders and remitters and mean changes in HRSD, VAS pain score, and ARSQ from week 0 to week 8. In addition to these point estimates, we will report the corresponding 95% confidence intervals. Similar analyses will be done on the sample of completers (i.e. those who complied with drug administration across all 8 weeks based on pill counts of at least 80%).

To examine the hypothesis that baseline pain level will be predictive of response to tianeptine, we will further investigate whether any single baseline pain battery score can be used to construct subgroups of subjects showing greater response to tianeptine. Based on the distribution of a given pain battery score and preliminary exploratory bivariate modelling, we will dichotomize the pain score (low/high) and compare response/remission rates and change scores for HRSD between the groups corresponding to low and high pain battery score. We will

report effect sizes corresponding to differences in response/remission rates and differences in HRSD change scores. Exploratory analyses will employ multivariable logistic (for response/remission outcomes) and linear (for HRSD change score) regression to investigate whether combinations of baseline pain scores can be used to identify subgroups who will show greater response to tianeptine. Additional analyses will employ multivariable logistic and linear regression to investigate associations between baseline neuropsychiatric and/or MRI measures and remission/response or HRSD change score. To take advantage of the fact that HRSD and TESS are collected at each study visit (8 post-baseline measures), we will also employ linear mixed effects models to investigate the effects of each baseline pain battery score on HRSD and TESS over time.

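### The 5% level and power in Section 5.1 assume one given pain score at a median split; Section 5.2 screens the battery with no fixed score, cut or lead outcome, and the 30-point power claim is too general

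*Combined protocol and SAP*

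**What the plan says.** Section 5.1 powers the subgroup comparison "assuming a median split" of 37 and 38 subjects "for a given physical or emotional pain battery score". At a two-sided 5% level it makes three statements:

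- more than 80% power for a low/high difference in HRSD change of d = 0.66;
- more than 80% power for differences of at least 30 percentage points in response or remission;
- for 10% v 40%, "we have 86% power to find this statistically significant at the 5% significance level".

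Section 5.2 describes the analysis as follows: "we will further investigate whether any single baseline pain battery score can be used to construct subgroups of subjects showing greater response to tianeptine". The low/high cut comes from two sources: "Based on the distribution of a given pain battery score and preliminary exploratory bivariate modelling, we will dichotomize the pain score (low/high". The plan will then "compare response/remission rates and change scores for HRSD between the groups corresponding to low and high pain battery score", and report effect sizes for the differences. No score, cut or lead outcome is named for this step, and no adjustment is given. The only multiplicity control in the document is the Bonferroni correction for MRI regions in Section 2.3.

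Section 5.2 applies the word exploratory to the preliminary modelling and to the regressions on combinations of scores ("Exploratory analyses will employ multivariable logistic"). It does not apply it to the single-score comparison.

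**The concern.** The procedure that is powered is not the procedure that is described. Section 5.1 treats the score and the cut as given, so there is one test per outcome. Section 5.2 leaves both open and looks across the battery for a score that works. Anyone who reads a subgroup found in this way against the Section 5.1 level will understate the false-positive risk, and the effect size of the best-looking score will tend to be too large.

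This matters because Section 2.4 introduces the idea that pain sensitivity predicts response to tianeptine with the words "The hypothesis under investigation in this study", and Section 1 names biomarker-based selection of patients as an ultimate goal. A chance finding here could decide who is selected for a later study.

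**Working it through.** **1. Reproduce Section 5.1 (n = 37 and 38, two-sided alpha 0.05).**

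HRSD change: noncentrality = d × √(n1·n2/(n1+n2)) = 0.66 × √(37×38/75) = 0.66 × 4.330 = 2.858. With 73 degrees of freedom the critical t is 1.993, and the noncentral t gives power 80.5%. The statement holds.

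Proportions: power = Φ{(|p1−p2| − 1.96·SE0)/SE1}, where SE0 = √[p̄(1−p̄)(1/37+1/38)] and SE1 = √[p1(1−p1)/37 + p2(1−p2)/38]. For 10% v 40%, p̄ = 0.252, SE0 = 0.1003 and SE1 = 0.0935. So (0.30 − 1.96×0.1003)/0.0935 = 1.106, and power is 86.6%. The plan's 86% is reproduced.

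**2. Test the general 30-point statement with the same formula.**

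| Rates | Power (pooled) |
|---|---|
| 10% v 40% | 86.6% |
| 15% v 45% | 82.2% |
| 20% v 50% | 78.9% |
| 30% v 60% | 75.2% |
| 35% v 65% | 74.8% |

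At 20% v 50% the answer depends on the formula: an unpooled variance gives 81.9%, an exact calculation for the chi-square test 79.5%. At 35% v 65% all three fall short (74.8%, 77.7% and 78.6%).

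**3. Count the candidate scores.** Section 5.2 does not list the battery. The baseline list in Section 2.5 names 4 pain tests (BPI, ARSQ, C-SSRS, Psychache). Section 2.4 lists 3 physical tests plus 9 under emotional pain and interpersonal wellbeing, 12 in all. The text and table of Section 2.5 add others, including the UCLA Loneliness Scale and a body-pain VAS. I use 4 and 12 as illustrations; neither is a bound.

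**4. False-positive rate with the cut held at the median.** For k independent scores and one outcome, the chance of at least one p<0.05 is 1 − 0.95^k: 18.5% for k = 4 and 46.0% for k = 12. Pain scores will be correlated, so I simulated 75 subjects, equicorrelated normal scores (r = 0.3, 0.5, 0.7) unrelated to HRSD change, and a pooled t test at 37/38:

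| Result under no effect | 4 scores | 12 scores |
|---|---|---|
| At least one p<0.05, two-sided | 16–18% | 32–43% |
| At least one p<0.05 with high pain doing better (nominal 2.5%) | 8–9% | 16–23% |
| Mean of the largest high-minus-low d | 0.17–0.22 | 0.27–0.34 |

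**5. Three outcomes.** This needs an assumed HRSD distribution (baseline mean 26, SD 5, minimum 16; fall with SD 8 and mean 6 to 14), and the plan names no test. One score with three outcomes gives 8–10% with Fisher tests for the two proportions or 11–14% with Pearson. Four scores give 24–32% or 33–39%.

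**6. Cut chosen against outcome.** One score, HRSD change only, best cut between the 25th and 75th percentiles: about 25% two-sided. The plan does not state such a search, so this is a ceiling for one reading of it.

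**7. Power if the level is protected.** At d = 0.66, power is 71.5% at alpha 0.025, 61.7% at 0.05/4 and 46.5% at 0.05/12. The d needed for 80% power is about 0.73, 0.79 and 0.88.

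**The case against.** The strongest reply is that this step is exploratory in all but name. Section 5.2 speaks of investigating further and of reporting effect sizes. It gives no test, alpha or decision rule for the step, and the comparison is not among the endpoints in Section 4. Much of that stands, and it is why the lead fix is a relabelling. What it does not answer is Section 5.1, which promises statistical significance at 5% with stated power for this comparison. Reporting effect sizes does not remove the upward bias in the largest one either.

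Three stronger readings are tempting, and the document does not support them:

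- **That the plan optimises the cut on outcome.** The variables in the preliminary modelling are not named. A cut set from the score's distribution alone would not inflate the error rate. The figures in step 4 use no cut search, so the point does not depend on this reading.
- **That 12 scores is the known or maximum size of the battery.** Section 2.5 adds instruments, while the Section 2.4 heading covers wellbeing as well as pain. The true count could lie on either side.
- **That the trial's main result is compromised.** HRSD change in the whole sample (Section 4) involves no pain score or split.

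One could also say that HRSD change, as the primary endpoint, leads here by default. Section 5.2 does not say so. If it did, the 16–18% and 32–43% would remain, since they already use that outcome alone.

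**Conclusion.** The point holds. The Section 5.1 level and power apply to one pre-specified score at a median split, and not to a subgroup found by the Section 5.2 step. On HRSD change alone the false-positive chance is roughly three times nominal with 4 scores and six to nine times with 12. This rests on the illustrative counts, assumed correlations of 0.3–0.7 and normal scores. Several outcomes, or a cut that used outcome data, would raise it further.

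As a separate matter, the claim of more than 80% power for any 30-point difference is wrong as a general statement, even for one median split. It is right for the example given.

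The defect is a mismatch between two sections on the study's central hypothesis. It does not touch the primary endpoint.

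**What to change.** **Lead option.** In Section 5.2, label the whole single-score low/high step exploratory, list the scores in the battery, fix the cut at the median (or set it without outcome data), and report the effect size and confidence interval for every score, not only the best. In Section 5.1, either say that the level and power apply to one pre-specified score only, or withdraw them for this step. Limit the 30-point statement to the 10% v 40% example. The cost is wording and a weaker stated claim: the pain hypothesis would have no confirmatory test.

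**Alternative, only if the choice can still be made and dated without looking at outcome data.** Name one physical and one emotional score, with the median split, HRSD change as the tested outcome and Holm adjustment over the two; label everything else exploratory. VAS pain and the ARSQ are candidates, since Section 4.1 already uses them, but the Section 2.5 table lists two VAS instruments and the plan must say which. Restate power as 71.5% at d = 0.66 for the first Holm step, or 80% at d of about 0.73.

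The condition may be hard to meet. Section 2.1 reports 28 subjects already entered, and Section 7.3 has the statisticians reporting regularly to investigators on accrued data. All subjects receive tianeptine, so even a controlled test could not separate prediction of drug response from general prognosis.

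### Section 5.2's exploratory combination models have no limit on terms, shrinkage or internal validation, so a subgroup cut from the fitted score can show a sizeable response difference from noise alone.

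*Combined protocol and SAP*

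**What the plan says.** Section 5.2 has two layers of predictor analysis. The first takes one baseline pain score at a time, dichotomises it, and compares response, remission and HRSD change between the low and high groups. The second, labelled exploratory, uses multivariable logistic regression for response and remission and linear regression for HRSD change, to see whether "combinations of baseline pain scores can be used to identify subgroups who will show greater response to tianeptine". A further sentence plans the same kinds of model for "associations between baseline neuropsychiatric and/or MRI measures and remission/response or HRSD change score".

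For the combination models the plan does not state which scores may enter, how many, how they are chosen, or how a combined score would be turned into a subgroup. Neither section 5.2 nor any other section mentions penalisation, cross-validation, bootstrap or optimism correction.

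The pool of candidate scores is in section 2.4: three physical pain tests and nine "emotional pain and interpersonal wellbeing tests", 12 instruments in all. Section 2.5 adds a loneliness scale, which would make 13. Section 2.5 also gives a narrower list under the pain labels: one physical instrument and three emotional ones.

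Section 5.1 gives the sample size and the power for a low/high comparison on a single score. It gives no operating characteristics for a fitted combination.

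**The concern.** A regression fitted to many scores in few patients chooses the weights that best separate those patients. Judged in the same patients, the resulting score looks better than it would in new ones, even when no score carries information. This differs from multiplicity across single-score tests: one fully pre-specified combined model has the same optimism in its raw fit measures.

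The information per term is thin. At 25% response there are 0.25 × 75 = 18.75 responders, or 18.75 / 12 = 1.6 per score if all 12 enter. At 40% there are 30, or 30 / 12 = 2.5 per score.

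The Introduction lists among the project's goals an assessment battery for opioid-signalling deficits and, ultimately, better response in a biomarker-selected subgroup. A combination that separates patients only by overfitting could be carried into later patient selection. The exploratory label warns the reader to be cautious but does not show how much of a reported separation is optimism.

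**Working it through.** **Inputs from the documents (section 5.1 unless noted).**
- Size: "With total sample size of 75 subjects".
- Error rate: "using a 2-sided test with a 5% significance level".
- Split: "assuming a median split (low/high", 37/38, stated for a single score.
- Example: "if depression response/remission is 10% in the low pain group and 40% in the high pain group".
- Stated power: "we have 86% power to find this statistically significant at the 5% significance level".
- Candidate scores: 3 + 9 = 12 (section 2.4).

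**Assumed, because the documents do not give them.** The true overall response rate, the number of scores entered, and a median split of the fitted score.

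**Step 1: reproduce the plan's figure.** Normal approximation for two proportions, null variance pooled:
- Pooled rate = (37 × 0.10 + 38 × 0.40) / 75 = 18.9 / 75 = 0.252.
- Null SE = √[0.252 × 0.748 × (1/37 + 1/38)] = 0.1003.
- Alternative SE = √[0.10 × 0.90 / 37 + 0.40 × 0.60 / 38] = 0.0935.
- z = (0.30 − 1.96 × 0.1003) / 0.0935 = 1.106, so power = 86.6%.

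The stated 86% reproduces. The pooled rate also gives the only overall response rate that can be derived from the documents, about 25%.

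**Step 2: expected R-squared under the null.** For a linear model with k unrelated scores and n patients, E(R²) = k / (n − 1). For k = 12 and n = 75 this is 12 / 74 = 16%; for k = 6, 6 / 74 = 8%. It does not depend on the response rate. The true value is 0.

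**Step 3: apparent response difference under the null.** Simulation, 1,000 to 1,500 trials per setting for 12 scores: draw k scores unrelated to response for 75 patients, fit an unpenalised logistic model with all k, split at the median fitted score, and record high-half minus low-half response. Then apply the same coefficients to 75 new patients.

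| Scores entered | True response | Mean apparent difference (points) |
|---|---|---|
| 12 | 20% | 25 |
| 12 | 25% | 27.5 (5th to 95th percentile 15 to 39) |
| 12 | 30% | 29 |
| 12 | 40% | 32 (17 to 47) |
| 12 | 50% | 33 |
| 6 | 25% / 40% | 19 / 22 |
| 4 | 25% / 40% | 15 / 17 |
| 1 | 25% | 7 |

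Wherever the coefficients were applied to new patients, the mean difference was within 1 point of 0. Correlation of 0.3 or 0.6 between scores hardly changes the 12-score results (27 at 25% response, 32 at 40%). The apparent AUC with 12 scores averages 0.76 at 25% response and 0.73 at 40%; the truth is 0.50. At 10% true response, which could apply to remission, the 12-score difference is 16 points.

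**Step 4: what the model tests do.** With 12 noise scores, the linear model's overall F test rejects in 5% of null trials and mean adjusted R-squared is 0.00. The logistic likelihood-ratio test rejects in about 10 to 13% at 20 to 50% response (22% at 10% response). By contrast, a chi-square test between the fitted-score halves, if someone ran it, gives p < 0.05 in 83 to 89% of null trials at 20 to 50% response.

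**The case against.** The case for leaving the plan alone has four parts.

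1. The models are labelled exploratory, and no endpoint in sections 4, 4.1 or 4.2 uses them. The goal about the assessment battery is itself framed as exploring heterogeneity. This stands and limits the weight of the point.
2. Twelve scores is a ceiling. Some of the 12 are stress, shyness or social-support scales, and section 2.5 attaches the pain labels to only four. This stands, and is why results for 4 and 6 scores are shown. The false difference shrinks but does not vanish, and choosing a smaller set after seeing the data would not remove it.
3. Section 5.2 does not say that results will be judged by apparent AUC, raw R-squared or a split of the fitted score. This stands too: the size of the problem is conditional on such a report. But the stated purpose is to identify subgroups, and the plan offers no other way of judging that.
4. Standard inference already allows for the number of terms. This is largely right (step 4). A reader might infer that the combined model will look predictive whether or not it is. The overall tests do not support that.

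A reader might also infer that noise produces 32 points and so beats the 30-point difference the trial is powered to find. The documents do not support that either. The 32 needs about 40% response, all 12 scores and a median split of the fitted score; at the 25% average of section 5.1's own example it is about 28. The 30 points in section 5.1 is for a single score, for which noise gives about 7 on average.

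**Conclusion.** The gap is real and should be closed, but its size is conditional. Section 5.2 sets no limit on terms, no shrinkage and no internal validation for models meant to identify subgroups in the same 75 or fewer patients. If a subgroup is cut at the median of the fitted score and judged in those patients, the mean false difference is:
- about 25 to 33 points with all 12 scores at 20 to 50% true response, and about 28 at 25%;
- about 19 to 22 points with 6 scores, and 15 to 17 with 4, at 25 to 40% response.

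For HRSD change, 12 noise scores give an expected R-squared of 16%. The fault lies in apparent separation and fit; the overall model tests are only modestly inflated.

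The same gap touches the neuropsychiatric and MRI models, but no size can be put on it there. The documents give neither the number of MRI measures nor a clear number of scanned patients, and that sentence speaks of associations, not subgroups. The primary endpoint is unaffected.

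**What to change.** Amend section 5.2 for the combination models as follows.

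- Name a small set of terms in advance, or fit with ridge or elastic net.
- Report bootstrap optimism-corrected or repeated cross-validated AUC (response, remission) and R-squared (HRSD change) alongside any apparent fit. Even 4 pre-named terms leave 15 to 17 points of false separation, so limiting terms does not replace this step.
- Put any selection of scores, and any choice of cut, inside the resampling.
- If a predicted-responder subgroup is described, estimate its response difference from out-of-fold predictions.

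The cost is a short change of SAP wording and modest programming, with no new patients, visits or data. The downside is that headline performance will be lower than the apparent figures.

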5.3 Subject Population(s) for Analysis

Subjects will be adult outpatients with treatment-resistant MDD who are without contraindications for neuroimaging procedures or tianeptine administration.

6. Safety and Adverse Events

6.1 Definitions

Adverse Event: *Adverse event* means any untoward medical occurrence associated with the use of a drug in humans, whether or not considered drug related.

Life-threatening adverse event or life-threatening suspected adverse reaction. An adverse event or suspected adverse reaction is considered "life-threatening" if, in the view of either the investigator or sponsor, its occurrence places the patient or subject at immediate risk of death. It does not include an adverse event or suspected adverse reaction that, had it occurred in a more severe form, might have caused death.

Serious Adverse Event: *Serious adverse event or serious suspected adverse reaction.* An adverse event or suspected adverse reaction is considered "serious" if, in the view of either the investigator or sponsor, it results in any of the following outcomes: Death, a life-threatening adverse event, inpatient hospitalization or prolongation of existing hospitalization, a persistent or significant incapacity or substantial disruption of the ability to conduct normal life functions, or a congenital anomaly/birth defect. Important medical events that may not result in death, be life-threatening, or require hospitalization may be considered serious when, based upon appropriate medical judgment, they may jeopardize the patient or subject and may require medical or surgical intervention to prevent one of the outcomes listed in this definition. Examples of such medical events include allergic bronchospasm requiring intensive treatment in an emergency room or at home, blood dyscrasias or convulsions that do not result in inpatient hospitalization, or the development of drug dependency or drug abuse.

Suspected adverse reaction means any adverse event for which there is a reasonable possibility that the drug caused the adverse event. For the purposes of IND safety reporting, "reasonable possibility" means there is evidence to suggest a causal relationship between the drug and the adverse event. Suspected adverse reaction implies a lesser degree of certainty about causality than adverse reaction, which means any adverse event caused by a drug.

Unexpected adverse event or *unexpected suspected adverse reaction*. An adverse event or suspected adverse reaction is considered "unexpected" if it is not listed in the investigator brochure or is not listed at the specificity or severity that has been observed; or, if an investigator brochure is not required or available, is not consistent with the risk information described in the general investigational plan or elsewhere in the current application, as amended. For example, under this definition, hepatic necrosis would be unexpected (by virtue of greater severity) if the investigator brochure referred only to elevated hepatic enzymes or hepatitis. Similarly, cerebral thromboembolism and cerebral vasculitis would be unexpected (by virtue of greater specificity) if the investigator brochure listed only cerebral vascular accidents. "Unexpected," as used in this definition, also refers to adverse events or suspected adverse reactions that are mentioned in the investigator brochure as occurring with a class of drugs or as anticipated from the pharmacological properties of the drug, but are not specifically mentioned as occurring with the particular drug under investigation.

Adverse Event Reporting Period: The study period during which adverse events must be reported is normally defined as the period from the initiation of any study procedures to the end of the study treatment followup. For this study, the study drug follow-up is defined as 24 hours following the last administration of study drug (or the end of the study for those who must stop tianeptine but continue with the assessments).

Preexisting Condition: A preexisting condition is one that is present at the start of the study. A preexisting condition will be recorded as an adverse event if the frequency, intensity, or the character of the condition worsens during the study period.

General Physical Examination Findings: At screening, any clinically significant abnormality will be documented. At the end of the study, any new clinically significant findings/abnormalities that meet the definition of an adverse event will also be recorded and documented as an adverse event.

Abnormal Laboratory Values: A clinical laboratory abnormality will be documented as an adverse event if any one of the following conditions is met: (1) the laboratory abnormality is not otherwise refuted by a repeat test to confirm the abnormality, (2) the abnormality suggests a disease and/or organ toxicity, (3) the abnormality is of a degree that requires active management; e.g. change of dose, discontinuation of the drug, more frequent follow-up assessments, further diagnostic investigation, etc.

Hospitalization, Prolonged Hospitalization or Surgery: Any adverse event that results in hospitalization or prolonged hospitalization will be documented and reported as a serious adverse event unless specifically instructed otherwise in this protocol. Any condition responsible for surgery should be documented as an adverse event if the condition meets the criteria for an adverse event. Neither the condition, hospitalization, prolonged hospitalization, nor surgery are reported as an adverse event in the following circumstances: (1) Hospitalization or prolonged hospitalization for diagnostic or elective surgical procedures for a preexisting condition, (2) hospitalization or prolonged hospitalization required to allow efficacy measurement for the study, (3) hospitalization or prolonged hospitalization for therapy of the target disease of the study, unless it is a worsening or increase in frequency of hospital admissions as judged by the clinical investigator.

Known Side Effects of tianeptine:

Tianeptine is generally well tolerated and severe side effects are rare.¹⁻⁵ Tolerability in comparative clinical trials has been generally found to be better than tricyclic antidepressants and comparable to selective serotonin reuptake inhibitors.¹⁻⁵ Commonly reported side effects with an incidence between 1 and 10% include the following:¹⁻⁶

Gastrointestinal: nausea, vomiting, flatulence, constipation, abdominal pain, dry mouth, loss of appetite

Psychiatric and Central Nervous System: headache, dizziness, altered dreaming, drowsiness, insomnia, presyncope, tremors

Cardiovascular: palpitations, chest pain, hot flashes, tachycardia

Respiratory: difficulty breathing

Musculoskeletal: muscle pain, lower back pain

General: feeling of weakness, feeling of lump in the throat

